Acceptance and Commitment Therapy ("ACT"; Hayes et al., 2012) is an empirically supported treatment with "strong research support" for CP by the *American Psychological Association* (APA, 2013). The experience of injustice has recently been conceptualized within the ACT psychological flexibility model (Scott et al., 2013b). ACT has been shown to help improve functioning and quality of life despite pain, and could potentially help mitigate the impact of perceived injustice on adverse pain outcomes (e.g. disability, depressive symptoms). Given the evidence of the effectiveness of ACT with CP, there are increasing efforts to improve the accessibility of this type of treatment. In particular, internet-delivered versions of ACT for CP are promising because they offer a cost-effective treatment option that usually requires little support from a therapist, and can be widely accessed.

Despite promising results (Bring, Åsenlöf, & Söderlund, 2016; Trompetter et al., 2016), further studies are needed to evaluate the effects of self-help interventions like ACT, including on physical and emotional functioning (Brown et al., 2016, Eccleston et al., 2014). Given the recent nature of self-help interventions in a population with chronic pain, other studies need to support their effectiveness. In addition, there are no studies that compared a self-help Web-based ACT intervention to a bibliotherapy intervention (French, Golijani-Moghaddam, & Schröder, 2017).

Objectives:

Evaluate the effectiveness and change processes of a web-based intervention program with minimal therapeutic contact, compared to a bibliotherapy and an education program based on brochures in adults with suffering of chronic pain.

Hypothesis 1: It is expected that the web-based self-help intervention generates a significant reduction in pain-related disability greater than the control group (education).

Hypothesis 2: It is expected that the bibliotherapy self-help intervention by bibliotherapy will result in a significant reduction in pain-related disability (primary variable) greater than the control group (education).

Hypothesis 3: It is expected that a web-based intervention will be associated with a greater reduction in pain-related disability (the primary variable) than bibliotherapy.

Hypothesis 4: It is expected that self-help Web-based interventions will lead to a significant improvement in the quality of life above the control (education) group.

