Hypothesis 5: It is expected that bibliotherapy will significantly improved the quality of life superior to the control group (education).

Hypothesis 6: Self-help interventions are expected to result in a significant reduction in anxiety and depressive symptoms compared to the control (education) group.

Hypothesis 7: Self-help interventions with bibliotherapy are expected to result in a significant reduction in anxiety-depressive symptoms compared to the control (education) group.

Hypothesis 8: Results on primary (incapacity) and secondary variables (quality of life, anxiety-depression) will remain at 3 and 6 months and will be superior to education brochure (control group).

Hypothesis 9: The flexibility process is expected to be a mediator of change in the primary (disability) and secondary variables (quality of life, anode-depressive symptoms).

Participants and procedure: Recruitment will be done in collaboration with the Quebec Association of Chronic Pain (AQDC), the Quebec Pain Research Network (RQRD), the Quebec Society of Fibromyalgia (SQF), Migraine Quebec, the Pain Clinics of Quebec. Quebec (28 including the CHUM, distribution of maps and billboards) and social networks Facebook (Facebook page with paid advertising). Participants will be notified of the study via email. If they have an interest in the study, they will click on a link that will take them to the information and consent form and will be asked questions about the inclusion criteria.

- » Be over 18 years old Living in Quebec
- » Have a daily pain (greater than 4 out of 10) for more than three months that is not associated with cancer;
- » Have a reading and writing ability of French equivalent to a secondary 2;
- » Have Internet access at home and an email address;
- » Never have ACT-type psychotherapy or regular meditation in mindfulness, and have not read [name]'s book "Libérez-vous de pain par méditation et ACT";
- » Have a stable medication for at least one month, if necessary.
- » Being emotionally stable

If they do not meet the criteria, they will be refer to a resource page and will be asked to leave their name as needed to be referred to relevant resources. If people meet the inclusion criteria, they will be asked to complete the pre-test questionnaires, which will confirm their participation in the study.

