Desis: A randomized control group trial with a sample of 300 presenting chronic pain, ie 100 persons for each experimental groups (web-based and bibliotherapy) and 100 persons for control group (education brochure).

Arms:

- Web-based, N = 100
- Bibliotherapy, N = 100
- Education brochure, N = 100

The estimate includes four measurement times (before and after the intervention, and two times at follow up (after 3 and 6 months) to assess the impact of the intervention in the longer term. The proposal will include three conditions, a group receiving a self-help web-based intervention, a group receiving a book-based intervention and a group receiving pain education brochures. Participants in all three groups receive 15-minute telephone calls from psychology students before and at week 3, a weekly email explaining the tasks to be completed, a discussion forum, access to an assistant to answer questions of a technical nature. These components aim to support participants' therapeutic approach and adherence to treatment (van Ballegooijen et al., 2014). Here is the content of the meetings for the 8 modules or weeks

Content of each module.

Week 1	Information about pain and ACT
Week 2	Values
Week 3	Learning to meditate

Week 4	Committed action
Week 5	Willingness to have pain
Week 6	Defuse from thoughts
Week 7	Pacing
Week 8	Conclusion

Instruments: All questionnaires will be self-administered online following an email sent. A hyperlink will automatically direct them to the UQTR Interactive Question Banking (IBQ) website. The completion time is evaluated between 25 and 30 minutes for each measurement period.

Participants answered questions related to socio-demographic information such as their age, education, daily occupation, and annual income. Participants also answered a series of questions related to pain, such as the diagnosis of chronic pain and the use of pain relief medication. Notably, participants were asked to rate the average pain they experienced in the past week on a numerical rating scale ranging from 0 (*no pain*) to 10 (*unbearable pain*). According to previous research, this scale is a reliable measure of pain intensity

Primary variable:

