System Usability Scale (SUS; Brooke, 1996) is a usability questionnaire that has been adapted into French. It will be sent to participants in the Web-based intervention only after the eight weeks of the program in order to measure their level of satisfaction with the program. This questionnaire contains 10 items (eg: I find that the features of this online workshop are well integrated) and responds on a five-point Likert scale (not at all strongly agree). A question will be added to ask participants about the number of modules they have completed. This questionnaire will take less than two minutes to complete.

Follow up only (week 20 and 28):

Patient Global Impression of Change (PGIC, 5 items). This tool assesses the level of change in pain, functioning, quality of life and psychological well-being factors over the past three months. They are evaluated on a 7-point Likert scale from 0 (significantly increased) to 6 (significantly decreased). A fifth item evaluates pain relief in the past three months and is measured on an ordinal scale ranging from 0 (no relief) to 100 (complete relief). This tool is increasingly used to assess the impact of change in the lives of patients with chronic pain (1 minute).

Data analysis:

The sample size for this study is optimized to compare the expected results on post-treatment pain interference. In addition, we expect the effect size for the web-based group to be higher than for the bibliotherapy. Randomized trials using an ACT intervention for chronic, web-based pain reported effect sizes of $d = 0.33$ (Trompetter et al., 2014), $d = 0.56$ (Buhrman et al., 2013) and $d = 0.58$ (Lin et al., 2017) with respect to pain-related interference. Considering the attrition of about 25% (between pretest and stimulus), based on the calculations of Lin et al. (2014), to obtain a statistical power of 80% (5%) and to detect an average effect size ($d = 0.40$), which proves clinically satisfactory for this type of study, a sample of 100 participants per group (300 in total) is required according to our calculations on G^* power.

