Generalized linear models with a group-by-time interaction will be used to compare the time conditions of the ACT-guided group with bibliotherapy and education brochures. Dichotomous arrival points will be modelled using a binomial distribution and a log link while a normal distribution and identity link will be used in the case of continuous arrival points. The generalized estimating equations approach will take into account the correlation between measurement times. Contrasts, defined a priori based on research hypotheses, will be used to make comparisons between groups and different measurement times. The analyzes will be performed according to the intent to treat.

Considering the current waiting lists for accessing psychological services in the public system, the social relevance of developing the accessibility of a self-help intervention by the Web is undeniable. We hope that our statistical data will support the development of new practices in the management of patients with chronic pain. The innovation will provide access to effective therapy in a short time and at low cost with a cost-benefit ratio.

References

- American Psychological Association (2013). Chronic or persistent pain. Retrieved from <http://www.div12.org/psychological-treatments/disorders/chronic-or-persistent-pain>
- Bender, J. L., Radhakrishnan, A., Diorio, C., Englesakis, M., & Jadad, A. R. (2011). Can pain be managed through the Internet? A systematic review of randomized controlled trials. *Pain*, 152(8), 1740-1750.
- Bergeron, D. A. (2016). Effects of an Internet-delivered cognitive behavioural therapy programme on chronic pain patients. *Evidence-Based Nursing*; 2016 Jul, Vol 19 (3), pp 87, Electronic publication. doi:10.1136/ebnurs-2016-102305
- Boggs, M. J., Beck, A., Felder, N. J., Dimidjian, S., Metcalf, A. C., & Segal, V. Z. (2014). Web-Based Intervention in Mindfulness Meditation for Reducing Residual Depressive Symptoms and Relapse Prophylaxis: A Qualitative Study. *J Med Internet Res*, 16(3), e87. doi:10.2196/jmir.3129

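### The group-by-time GEE makes no baseline adjustment; using the pretest score as a covariate would add power to the between-arm contrasts on continuous outcomes at no cost in data.

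*Combined protocol and SAP*

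**What the plan says.** The statistical model is one paragraph in the Data analysis section. It says that "Generalized linear models with a group-by-time interaction will be used to compare the time conditions" between the ACT web group, bibliotherapy and education brochures. Continuous outcomes use a normal distribution with identity link. It adds that "The generalized estimating equations approach will take into account the correlation between measurement times", and that "Contrasts, defined a priori based on research hypotheses, will be used to make comparisons between groups and different measurement times". It does not list the model terms, name a working correlation or write out the contrasts.

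Other sections bear on the reading:

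- **Design paragraph:** "The estimate includes four measurement times (before and after the intervention", with two follow-ups. The pretest is thus one of the repeated outcomes.
- **Participants and procedure:** eligible people are told that "they will be asked to complete the pre-test questionnaires, which will confirm their participation in the study". Every participant therefore has a pretest score.
- **Objectives:** Hypothesis 1 expects that the web intervention "generates a significant reduction in pain-related disability greater than the control group (education"; Hypotheses 2 and 3 are worded similarly. This points to a between-arm difference in change.
- **Data analysis, sample size:** "The sample size for this study is optimized to compare the expected results on post-treatment pain interference", which leaves a between-arm difference at post-test possible.

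No pretest covariate and no common pretest mean appears anywhere.

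**The concern.** With the pretest as a response and a full group-by-time structure, the model estimates a separate pretest mean for each arm. If the pretest is completed before allocation, as the procedure suggests, those means differ only by chance. A model that leaves them free discards that knowledge.

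A contrast in change then carries the noise of the pretest difference at full weight. A contrast at post-test makes little or no use of the pretest. Adjustment gives the pretest its best weight.

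The stake is power, not validity. It applies to the between-arm contrasts on continuous outcomes (disability, quality of life, anxiety-depression). It does not extend to the mediation hypothesis or to dichotomous outcomes. Whether 100 per arm allows enough for attrition is a separate question.

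**Working it through.** **Inputs from the plan (Data analysis, sample size).** d = 0.40, 5% level, 80% power, 100 per arm, attrition of about 25%.

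**Assumptions.**
- The test is two-sided; sidedness is not stated.
- SDs are equal and set to 1.
- The attrition phrase, "Considering the attrition of about 25% (between pretest and stimulus", is unclear. I read it as loss by post-test, which leaves 75 of 100 per arm.
- Dropout is unrelated to outcome.
- The pre-post correlation r is not in the documents, so I show 0.3 to 0.8.

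**The plan's own figure.** n = 2(1.960 + 0.842)²/0.40² = 98.1, so 99 per arm; the t-test version gives 99.08, so 100. The stated 100 per arm is thus reproduced two-sided as a number of evaluable participants, with no baseline adjustment and no attrition allowance.

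**Per-arm variance of each contrast.**
- Change, efficient working correlation: (1 − r²)/75 + (1 − r)²/100
- Post-test, efficient working correlation: (1 − r²)/75 + r²/100
- Change, independence working correlation: 1/75 + 1/100 − 2r/100
- Post-test, independence working correlation: 1/75
- Pretest covariate, either working correlation: (1 − r²)/75 × (1 + 1/219), where the last factor allows for estimating the slope

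Then SE = √(2 × variance) and power = Φ(0.40/SE − 1.96).

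**Example at r = 0.5.** Change, efficient: 0.75/75 + 0.25/100 = 0.01250, SE 0.158, power 71.6%. Covariate: 0.01 × 1.0046 = 0.01005, SE 0.142, power 80.6%.

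**Power (%).**

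| r | Pretest covariate | Change, efficient | Post-test, efficient | Change, independence | Post-test, independence |
|---|---|---|---|---|---|
| 0.3 | 72.6 | 58.2 | 69.8 | 57.5 | 68.8 |
| 0.4 | 76.0 | 64.2 | 70.5 | 62.7 | 68.8 |
| 0.5 | 80.6 | 71.6 | 71.6 | 68.8 | 68.8 |
| 0.6 | 86.3 | 80.2 | 72.8 | 75.7 | 68.8 |
| 0.7 | 92.8 | 89.7 | 74.4 | 83.3 | 68.8 |
| 0.8 | 98.3 | 97.5 | 76.2 | 91.0 | 68.8 |

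**Gain from the covariate (percentage points, r = 0.3 to 0.8).**
- Over change, efficient: 14.4, 11.8, 9.0, 6.1, 3.1, 0.8
- Over post-test, efficient: 2.9, 5.5, 9.0, 13.5, 18.4, 22.1
- Over change, independence: 15.2, 13.3, 11.8, 10.6, 9.5, 7.2
- Over post-test, independence: 3.9, 7.2, 11.8, 17.5, 24.0, 29.5

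**As enrolment.** 100 × (change variance, efficient ÷ covariate variance) − 100 gives about 40, 32, 24, 18, 13 and 8 more people per arm over the same r.

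**Simulation check.** About 5,000 three-arm trials were simulated per r, with four visits, exchangeable true correlation and 25 per arm losing all post-tests at random. Empirical SDs at r = 0.3/0.5/0.7 were:
- change, exchangeable GEE: 0.186/0.160/0.125
- post-test, exchangeable GEE: 0.160/0.160/0.153
- pretest covariate: 0.156/0.144/0.118, identical under exchangeable and independence

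The covariate SDs imply 73/79/93% power, so at r = 0.5 I claim only about 80%.

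**Where the pretest goes matters.** A smaller simulation (150 two-arm trials per r) added the covariate but kept the pretest rows as responses. It gained nothing: SE 0.184 against 0.183 at r = 0.3, and 0.158 against 0.157 at r = 0.5.

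**The case against.** **The plan is silent rather than wrong.** The paragraph lists no model terms, so it does not rule out adjustment, and the argument needs the pretest to precede allocation, which is only suggested. Both points are true. But nothing commits the analysis to adjustment, and the text as it stands describes an unadjusted repeated-measures model.

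**GEE already uses the pretest.** It does, as a response. The efficient-correlation columns give full credit for that and still show a gain.

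**The largest gains rest on less natural readings.** This stands. Gains of 24 to 30 points need an independence working correlation with a post-test contrast. The hypotheses point to the change contrast; with an efficient correlation the gain there is about 3 points at r = 0.7 and under 1 at r = 0.8. With neither the contrast nor the working correlation fixed, however, the covariate form protects against the unfavourable choices.

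**The covariate model loses something.** A GEE fitted to the three later times cannot directly test within-arm pre-to-post change, and it drops participants with no later score. This also stands, but Hypotheses 1 to 3, which drive the contrasts for the primary outcome, compare arms. The four-time model with equal pretest means keeps both.

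**Severity.** The planned analysis is valid, so an optional grade is arguable. I would still ask for the change, because it costs almost nothing and, at mid-range r, moves power from about 70% to the plan's 80% target.

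**Conclusion.** The point holds as an efficiency finding. Under the stated assumptions the covariate form is more precise than both candidate contrasts, under both working correlations, for any r from about 0.1 to 0.98. At r = 0.5 the gain is about 9 points with an efficient working correlation and about 12 with independence.

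The direction is secure. The size is not, because it depends on r, on which contrast is meant and on the working correlation, and the documents give none of these. The gain over the change contrast fades as r approaches 1; the gain over the post-test contrast fades as r approaches 0. The change should be made, although the planned analysis is not invalid without it.

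**What to change.** For continuous outcomes:

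1. Fit the GEE to the three post-randomisation times only, with the pretest score as a covariate whose slope may differ by time. The pretest must leave the response vector.
2. Name the a priori between-arm contrasts and test them in that model.
3. State that the pretest is completed before allocation.

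The alternative is to keep all four times and constrain the pretest means to be equal across arms, but only with a stated non-independence working correlation. Under independence the constrained model reduces to the raw post-test difference (about 69% power) and loses about 7, 15 and 22 points to the change contrast at r = 0.6, 0.7 and 0.8.

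The cost is a few lines of SAP wording and standard software, with no new data or recruitment. Estimating the slope costs about 0.2 power points or less. Participants with no post-randomisation score do not enter the covariate model, so the SAP should say how this fits its intent-to-treat statement. If within-arm pre-to-post change is also wanted, the four-time constrained model supplies it.

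### About 25% loss is expected by post-test, but the GEE analysis has no working correlation and no missing-data method, so the BPI contrasts are exposed if loss is outcome-related and differs by arm

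*Combined protocol and SAP*

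**What the plan says.** The design section plans "four measurement times (before and after the intervention, and two times at follow up (after 3 and 6 months") in three arms: "ie 100 persons for each experimental groups (web-based and bibliotherapy) and 100 persons for control group (education brochure"). All questionnaires are self-completed online after an email, and completing the pretest confirms entry. Someone who stops responding therefore has a pretest score and nothing later.

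Attrition appears only in the sample-size paragraph of the Data analysis section: "Considering the attrition of about 25% (between pretest and stimulus"). The last quoted word is read here as post-test, an apparent translation slip. No rate is given by arm or for the 3- and 6-month visits.

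The model paragraph of that section specifies a generalized linear model with a group-by-time interaction, normal with identity link for continuous outcomes and binomial with log link for dichotomous ones. On estimation it says "The generalized estimating equations approach will take into account the correlation between measurement times". A priori contrasts follow the hypotheses, and "The analyzes will be performed according to the intent to treat". The document states no working correlation, missingness assumption, weighting, imputation or sensitivity analysis.

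**The concern.** Ordinary GEE uses the questionnaires that come back. It is guaranteed consistent only when being missing does not depend on outcomes, including the pretest score already observed. Accounting for correlation, the plan's only stated reason for GEE, does not by itself deal with missing data. Intent to treat settles who is analysed and in which arm, but it supplies no missing post-test score.

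Hypotheses 1, 2, 3 and 8 all rest on group comparisons of pain-related disability. The arms ask for different work (a web programme, a book, brochures), so the kind of person who stops responding could differ between them. If people with high interference stop responding in one arm and not in another, that arm's later mean can look better than it is. With the opposite selection it can look worse. How much of this reaches the estimate depends on a working correlation that the plan leaves open and that could be chosen after the data are seen.

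**Working it through.** **Inputs from the plan.** d = 0.40 (so SD = 1), 100 per group, about 25% loss by post-test, four visits, three arms, normal model with identity link.

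**The plan's own figure.** A two-sided 5% test with 80% power gives n = 2(1.96 + 0.8416)²/0.40² = 98.1, so 99 per group; the t-test version gives 99.08, so 100. The stated 100 thus matches a two-sided calculation with no attrition allowance. That is a separate matter, and nothing below depends on it.

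**Assumptions, not in the documents.** The pretest-post correlation ρ is 0.3, 0.5 or 0.7. Correlations of pretest with 3 and 6 months are 0.9 and 0.8 times that, and later visits correlate 0.6 to 0.7. A further 10% of those remaining is lost at each follow-up. In the web arm, leaving has odds ratio 2 per SD of the last observed BPI; in education it is random. The true web-minus-education effect is -0.40 at every later visit.

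**Post-test by hand, independence working correlation.** The web post-test mean is then the plain mean of those who stay. With odds ratio 2 and 25% loss, stayers have mean standardised pretest m = -0.159 (numerical integration of the logistic retention curve over a standard normal). Bias = ρ × m:

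- ρ = 0.3: 0.3 × -0.159 = -0.048, estimate -0.448
- ρ = 0.5: 0.5 × -0.159 = -0.080, estimate -0.480
- ρ = 0.7: 0.7 × -0.159 = -0.111, estimate -0.511

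**Large-sample simulation, 400,000 per arm, same assumptions** (range over the three correlations):

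| Working correlation | Post-test | 6 months |
|---|---|---|
| Independence | -0.45 to -0.51 | -0.51 to -0.57 |
| Exchangeable | -0.37 to -0.41 | -0.38 to -0.39 |
| Unstructured (true covariance supplied) | about -0.40 | about -0.40 |

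With the same selection in both arms, all three structures give about -0.40. With selection reversed in the web arm, independence gives -0.29 to -0.35 at post-test and -0.24 to -0.28 at 6 months, so the direction cannot be predicted.

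**All three primary contrasts.** A second simulation used 150,000 per arm, correlation 0.6 throughout, both ACT arms 0.40 better than education, leavers with a pretest only, and working correlations estimated from the data. Entries are bias at post-test in SD units, in the order web-education, bibliotherapy-education, web-bibliotherapy. Simulation error is about 0.005. Rates and log-odds slopes per SD are for education/bibliotherapy/web.

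| Loss depends on | Rates (%) | Slopes | Independence | Exchangeable or unstructured |
|---|---|---|---|---|
| Nothing | 15/25/35 | 0/0/0 | about 0 | about 0 |
| Pretest | 25/25/25 | 0.7/0.7/0.7 | about 0 | about 0 |
| Pretest | 15/25/35 | 0.7/0.7/0.7 | -0.071, -0.039, -0.032 | about 0 |
| Pretest | 25/25/25 | 0/0.35/0.7 | -0.095, -0.050, -0.044 | about 0 |
| Pretest | 15/25/35 | 0/0.35/0.7 | -0.137, -0.057, -0.081 | about 0 |
| Unseen post-test | 25/25/25 | 0.7/0.7/0.7 | about 0 | about 0 |
| Unseen post-test | 25/25/25 | 0/0.35/0.7 | -0.158, -0.084, -0.073 | -0.10, -0.054, -0.046 |
| Unseen post-test | 15/25/35 | 0/0.35/0.7 | -0.220, -0.084, -0.136 | -0.140, -0.054, -0.086 |

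The last two rows show what a correlated structure can and cannot do. When loss depends on the unseen post-test score, the pretest recovers only a fraction ρ² = 0.36 of the bias. For web-education that leaves 0.64 × -0.158 = -0.10 and 0.64 × -0.220 = -0.14.

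**The case against.** The best defence is that a plan which says GEE accounts for the correlation between visits most naturally means a correlated working structure, not independence. Under exchangeable, the one-arm scenario moves the post-test estimate by at most about 0.03 SD. The rough standard error with 75 completers per arm is √(2/75) = 0.16, so that bias is under one-fifth of a standard error. All arms get the same calls, weekly emails, forum and technical help. Because questionnaires arrive by email, stopping the programme need not mean not answering. That GEE would be unweighted is inferred from silence; the plan does not forbid weights or imputation.

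All of this stands, and it limits what can be said. A reader might infer any of the following, and the documents support none of them:

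- **Unequal withdrawal between arms biases every primary contrast.** Unequal rates with random loss gave essentially no bias, nor did the same mechanism and rate in every arm.
- **The effect will be overstated.** The shifts under independence (0.05 to 0.11 SD at post-test, 0.11 to 0.17 at 6 months) need that structure and an assumed selection pattern, and the sign can reverse.
- **Bias grows over follow-up.** That appeared under independence; under exchangeable the 6-month estimate stayed within about 0.02 SD of -0.40.
- **GEE must be abandoned.** For continuous outcomes an unstructured working correlation removed the bias wherever loss depended on observed scores.

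The defence does not remove the gap. Robust standard errors under independence would also fit the plan's sentence, and no correlated structure rescues arm-differing loss that depends on unseen scores.

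**Conclusion.** The concern holds in a conditional form. With about a quarter of post-test scores expected to be missing, the plan relies on a method whose general validity needs missingness unrelated to outcome, and it leaves open the setting that decides how far the primary contrasts are exposed. If loss is outcome-related and differs by arm, the post-test shift ranges from about zero (loss driven by observed scores, correct unstructured correlation) to 0.22 SD (loss driven by unseen scores, unequal rates, independence). The latter is 0.22/0.40 = 55% of the planning effect. These sizes rest on assumed odds ratios, correlations and arm-specific rates; only the overall 25% and d = 0.40 come from the plan. This is a weakness in the primary analysis that should be fixed, not evidence that the trial's estimates will be biased.

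**What to change.** For BPI interference, WHOQOL and HADS, specify a likelihood-based repeated-measures model with all randomised participants, group, time, group-by-time, unstructured covariance and the same a priori contrasts. Acceptable alternatives are to keep GEE with a pre-specified unstructured working correlation, or to run it on data multiply imputed by arm from earlier scores. For any dichotomous endpoint, use imputed or inverse-probability-weighted GEE. State the missing-at-random assumption for the main analysis.

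Add one delta-adjusted sensitivity analysis by arm, giving people who left progressively worse imputed values than those who stayed and reporting how far the conclusion holds.

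Use the weekly disability item as an imputation predictor only if it is collected in all three arms. The Weekly journal section ties it to opening each module, so it may be missing for those who stop, and its use in the book and brochure arms is unclear.

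The cost is wording and a little more analysis work, with no new data or participants. The main analysis would still rely on missing at random and a correctly specified covariance, which is why the sensitivity analysis is needed.
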